19.1 DEFINITIONS

The following definitions are from the ISO 14155:2020 and MDCG 2020-10:

Adverse Event (AE) – An adverse event (AE) is any untoward medical occurrence, unintended disease or injury, or untoward clinical signs (including abnormal laboratory findings.) in subjects, users, or other persons, whether or not related to the investigational device and whether anticipated or unanticipated.

NOTE 1: This definition includes events related to the investigational medical device or the comparator.

NOTE 2: This definition includes events related to the procedures involved.

NOTE 3: For users or other persons, this definition is restricted to events related to the use of investigational medical devices.

Anticipated Adverse Events – Anticipated adverse events are adverse events that have been identified as adverse events related to the investigational device or study procedure. The anticipated events of this clinical investigation are outlined in tDCS Adverse Events Questionnaire (AEQ). The frequency and severity of anticipated AEs will be captured using AEQ.

Anticipated adverse events are:

- Headache
- Neck pain
- Scalp pain
- Tingling
- Itching
- Burning sensation
- Skin redness
- Sleepiness
- Trouble concentrating
- Acute mood change

Adverse Device Effect (ADE) – An adverse device effect (ADE) is any adverse event related to the use of an investigational device. This definition includes:

CONFIDENTIAL Page **50** of **69**

- Adverse events resulting from insufficient or inadequate instructions for use, deployment, implantation, installation, or operation, or any malfunction of the investigational medical device.
- Any event resulting from use error or from intentional misuse of the investigational medical device.
- "Comparator" if the comparator is a medical device.

Serious Adverse Event (SAE) – A Serious Adverse Event is an AE which:

- 1. Led to a death,
- 2. Led to serious deterioration in the health of the subject, users, or other persons that either resulted in:
 - a) A life-threatening illness or injury, or
 - b) A permanent impairment of a body structure or a body function including chronic diseases, or
 - c) In-patient or prolonged hospitalization, or
 - d) Medical or surgical intervention to prevent life threatening illness or injury or permanent impairment to a body structure or a body function.
- 3. Led to fetal distress, fetal death or a congenital abnormality or birth defect including physical or mental impairment (not anticipated in this study as pregnant women are excluded from the study).

NOTE: Planned hospitalization for any pre-existing condition, or a procedure required by the Clinical Investigation Plan, without a serious deterioration in health, is not considered a serious adverse event.

Serious Adverse Device Effect (SADE) – a Serious Adverse Device Effect is an adverse device effect that has resulted in any of the consequences characteristic of a serious adverse event.

Anticipated Serious Adverse Device Effect (ASADE) – an Anticipated Serious Adverse Effect is an effect which by its nature, incidence, severity, or outcome has been identified in the risk analysis report.

Unanticipated Serious Adverse Device Effect (USADE) – this is a serious adverse device effect which by its nature, incidence, severity, or outcome has not been identified in the current version of the risk analysis report. This is also referred to as an Unanticipated Adverse Device Effect (UADE) in the US. See Section 19.2.4 for details regarding determination and reporting requirements in the US.

Device Deficiency (DD) - A device deficiency is an inadequacy of a medical device with respect to its identity, quality, durability, reliability, safety, or performance. Device deficiencies include malfunctions, use errors, and inadequacy in the information supplied by the manufacturer including labelling.

Malfunction – Failure of an investigational medical device to perform in accordance with its intended purpose when used in accordance with the instructions for use or protocol.

Use Error – User action or lack of user action while using the medical device that leads to a different result than that intended by the manufacturer or expected by the user.

NOTE1: Use error includes the inability of the user to complete a task.

NOTE 2: Use errors can result from a mismatch between the characteristics of the user, user interface, task or use environment.

NOTE 3: Users might be aware or unaware that a use error has occurred.

NOTE 4: An unexpected physiological response of the patient is not by itself considered a use error.

NOTE 5: A malfunction of a medical device that causes an unexpected result is not considered a use error.

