9 BENEFIT-RISK ANALYSIS

9.1 RISKS

The study device will deliver a maximum of 2 mA tDCS for 30 minutes at a time. Published data has shown conventional sessions to be \leq 40 minutes at \leq 4mA, and the tolerability and dropout rates between sham and active stimulation groups are equal in the literature.

As of August 2021, the most common side effects reported in the literature and from post-market data on Flow FL-100 are:

Side Effect	% of users
Skin irritation, redness	0.80%

Table 4. Common side effects from Flow FL-100

Strong tingling, stinging, or itching	0.14%
Headache	1.1%
Increased tinnitus	0.45%

Most people also experience skin redness at the stimulation site which passes within 30 minutes after the stimulation. Small skin burns are also known from the literature due to the use of tap water instead of physiological saline to wet the stimulation electrodes¹¹. Therefore, Flow is delivered with disposable pre-moistened sponges so that the users do not need to handle saline themselves.

The tDCS studies in participants with MDD have reported mostly consistent adverse events with large studies on healthy participants¹². In addition to this, there have been four studies that have published the appearance of treatment-emergent mania/hypomania (TEM) in eleven cases total¹³. Most cases of TEM have been where tDCS has been combined with antidepressant drugs, which are known to increase the risk of a manic switch¹⁴. As such, a causal relationship has not been determined. The observed cases have also been mild and in general not required any intervention (correspondence with authors). In the internal data from over 3,000 Flow FL-100 users, no instance of TEM has been discovered or reported. In accordance with the recommendation from Antal et al. (2017), participants with a history of bipolar disorder will be excluded from this study due to their increased risk of manic switch. As an additional safety measure, the YMRS will be administered at each follow-up visit.

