11.7 EXPLORATORY ENDPOINTS

- Young Mania Rating Scale (YMRS) at 10 weeks.
- tDCS Adverse Events Questionnaire (AEQ) at 10 and 20 weeks
- Hamilton Anxiety Rating Scale (HAM-A) change at week 10.

- HDRS-17, MADRS, MADRS-s mean decrease, and remission and response rate at 20 weeks (after open-label) compared to open-label start and baseline.
- Correlation between MADRS and MADRS-s.
- Correlation between adherence to stimulation and HDRS-17/MADRS decrease in the active group at 10 weeks.
- Neuropsychological measure: verbal learning (Rey Auditory Verbal Learning Test (RAVLT) and information processing speed (Symbol-Digit Modalities Test (SDMT)
- Treatment acceptability questionnaire (TAQ) as developed by UEL. There is one form at baseline and another at week 10 and 20.
- The within-patient clinically meaningful improvement as defined as at least -3 points on the HDRS-17 scale. The percentage of subjects for each arm that reaches -3 points or more improvement and also the Cumulative Distribution Function Curves of Change in HDRS-17 Score from Baseline to Primary end-point by arm.

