18 CONCOMITANT MEDICATIONS/THERAPIES

For the purposes of this clinical study, only medications taken or administered for the following will be recorded *(Ensure medications reflected in incl/excl are listed here)*:

- Muscle relaxation;
- Other medications related to or given for the participant's MDD.

19 Adverse Event & Device Deficiency Reporting

Subjects will be carefully monitored during the study for possible adverse events (AEs) from the time they sign the Informed Consent Form to the time of study completion. All medical events and conditions prior to this time point are to be captured as medical history.

Any observed unanticipated AE will be fully investigated by the Investigator and classified in line with the definitions of ISO 14155:2020 below. The frequency and severity of anticipated AEs will instead be captured using the tDCS Adverse Events Questionnaire (AEQ).

All unanticipated adverse events that occur during this study will be recorded on the adverse event eCRFs and must include the following information at minimum:

- Event Description
- Date of Onset
- Date of Resolution
- Severity
- Seriousness
- Relationship to Study Device/Procedure
- Outcome

Adverse events will be reported and classified by the Investigator using the specific signs, symptoms or abnormal laboratory values, or medical diagnosis if no signs, symptoms, or abnormal laboratory values can be identified.

Significant new information and updates should continue to be captured in the subject's records and in the EDC as they become available and the adverse event should be followed until it is resolved or no further improvement is expected, or the subject is lost to follow-up.

Adverse events that meet the definitions of seriousness in Section 19.1 below should also be reported to the Sponsor per the instructions provided in Section 19.2.4 below.

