19.2.2 Assessment of Relationship to Use of the Investigational Device or Procedure

The relationship between the use of the medical device (including the medical - surgical procedure) or control procedure the occurrence of each unanticipated adverse event shall be assessed and categorized. During causality assessment, clinical judgment shall be used, and the Clinical Protocol shall be consulted, as all the foreseeable adverse events and the potential risks are listed and assessed there. The presence of confounding factors, such as concomitant medication/treatment, the natural history of the underlying disease, other concurrent illness or risk factors shall also be considered.

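### The undefined anticipated event of acute mood change lets a non-serious mood switch or abrupt worsening be recorded on the AEQ alone, without the onset, resolution and relatedness data that section 22.14 promises

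*Protocol*

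**What the plan says.** The label anticipated or unanticipated decides how a non-serious event is recorded.

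- Section 19, opening text, on unanticipated events: "All unanticipated adverse events that occur during this study will be recorded on the adverse event eCRFs". That form holds onset and resolution dates, severity, seriousness, relationship to device or procedure, and outcome.
- Same place, on anticipated events: "The frequency and severity of anticipated AEs will instead be captured using the tDCS Adverse Events Questionnaire (AEQ".
- Section 19.2.2 limits the causality step in the same way: "the occurrence of each unanticipated adverse event shall be assessed and categorized".
- Section 19.1 defines the class: "Anticipated adverse events are adverse events that have been identified as adverse events related to the investigational device or study procedure". It then lists ten items. Most are local sensations or symptoms such as tingling, itching and headache. The last is "Acute mood change", with no definition.
- Section 11.7 gives the timing: "tDCS Adverse Events Questionnaire (AEQ) at 10 and 20 weeks". Table 1 adds the early termination visit, which section 15.4 makes optional. Section 13.1 also names the AEQ at screening, before any stimulation has been given.
- Section 22.14 promises listings with relatedness, severity, onset and resolution for all events. These include listings of device-related events and of events in participants who stopped early.

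**The concern.** Sending tingling and redness to a questionnaire is a sensible economy. A mood term is different, because mood is the illness under study and mood switching is a risk that the protocol itself discusses. Section 9.1 cites "four studies that have published the appearance of treatment-emergent mania/hypomania (TEM) in eleven cases" and describes the observed cases as mild. Mild cases are the ones that the serious-event route would not pick up.

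If such a case is filed as an acute mood change, the protocol asks for no AE form, no dates and no investigator judgement of relatedness. That judgement matters here, since a mood change in a depressed participant may come from the illness, a concomitant drug or the device. The safety listings would then be incomplete for the psychiatric events that a regulator is likely to ask about first.

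**Working it through.** The point rests on the text. The plan has no figure to reproduce, so the passages are set side by side.

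**Step 1: the route on the wording.** A non-serious event classed as anticipated goes to the AEQ (19), yields frequency and severity only (19, 19.1), and falls outside the required investigator assessment (19.2.2). Section 22.14 needs relatedness, onset and resolution for all events. The AEQ, as described, supplies none of the three. The sections conflict for every anticipated event, and the conflict matters most for the mood term.

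**Step 2: whether relatedness could be presumed.** By the 19.1 definition, anticipated events are already regarded as device- or procedure-related. On that reading each one would enter the device-related listing without individual assessment. Onset and resolution would still be missing, and a mood change in this population is a poor candidate for a blanket presumption.

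**Step 3: what the other safeguards require.**
- *Mania rating scale (YMRS).* It is given at weeks 1, 4, 7, 10 and 20 and at unscheduled visits. Section 14 says it covers the previous 48 hours. The scheduled blinded-phase visits therefore look back over 4 × 2 = 8 of 70 days (11%), and the week 20 visit over 2 of the next 70 days (3%). Episodes longer than 48 hours are more likely to overlap a window than these shares suggest, but an episode between visits can still be missed. Section 22.9 summarises the scale as a continuous exploratory score, and no section ties a result to an AE record.
- *AE review at visits (13.2 to 13.5).* New or updated events are to be recorded, but section 19 governs how, and it sends anticipated ones to the AEQ.
- *Clinical Events Committee (19.4).* It covers all AEs. The next sentence selects events for review largely by seriousness and relatedness category. An unrated event might be placed under unknown relationship, but 19.4 does not say so, nor what record the committee would receive if no AE form exists.
- *Withdrawal rules (12.3, 15.2) and recording of the reason (15.5).* They document why a participant left. They do not call for an AE form.
- *Serious events (19.2.4).* They are reported whether anticipated or not, so only non-serious events are affected.

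**Step 4: the other differences between 9.1 and 19.1.** Tinnitus (0.45% of users, Table 4) and burns ("Small skin burns are also known from the literature") appear in 9.1 but not in 19.1, and neither does mania. An event off the list is unanticipated, so it gets the AE form and the causality assessment. These omissions lead to fuller recording.

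**Step 5: how many events.** The protocol gives no rate of mood switching for a trial population, so the rates below are assumptions. With 1:1 allocation, the active arm has 270 / 2 = 135.
- Section 9.1 reports no case in over 3,000 users. The rule of three gives an upper 95% bound near 3 / 3,000 = 0.1%, and 135 × 0.001 = 0.14 events. That experience rests on cases discovered or reported, so it may run low.
- Assumed 0.5%, 1% and 3%: 135 × 0.005 = 0.7, 135 × 0.01 = 1.4, 135 × 0.03 = 4.1 events.

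The range is about 0.1 to 4 switches. Abrupt worsening would add to this by an amount that the documents do not allow one to estimate.

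**The case against.** The strongest reply is that psychiatric safety here does not depend on the AEQ. The YMRS, HDRS-17 and C-SSRS are done at every follow-up visit. A 30% rise in HDRS-17 counts as treatment failure and leads to withdrawal, current mania leads to discontinuation, and dropout data are presented separately. The mood term sits among items that are mostly transient sensations, and 19.1 ties the list to the AEQ, whose wording is not shown and may be narrower. Nothing says that clinician-detected hypomania must be coded as an acute mood change.

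Much of this stands. It makes a wholly unseen switch unlikely when it overlaps a visit, and it limits the harm. It does not supply the missing record, because none of these provisions requires an AE form with dates and relatedness. Nor does anything prevent coding under the broad term.

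Two stronger readings are tempting, and neither is supported. A reader might infer that leaving mania, tinnitus and burns off the list causes the gap. The effect is the reverse (step 4), and the absence of mania fits the 19.1 definition because 9.1 treats causality as unproven. A reader might also infer that causality review is bypassed altogether. Only the investigator's step in 19.2.2 is, since 19.4 gives the committee all AEs.

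**Conclusion.** The gap is real but narrow. As written, a non-serious hypomanic switch or abrupt worsening can be classed under an undefined anticipated term and reach the report without onset, resolution or an investigator's relatedness judgement, contrary to 22.14. This rests on the wording of 19, 19.1 and 19.2.2, and on the assumption that the AEQ does not itself narrow the term or collect dates.

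The documents do not show that the device's psychiatric safety profile will be understated, only that the recording rules permit it. The number of switches concerned is small (about 0.1 to 4 in the active arm under the assumed rates). With counts that low, each case carries weight, but the finding does not depend on them. The primary efficacy analysis is unaffected. The mismatch over tinnitus and burns is minor and no part of the cause.

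**What to change.** - In 19.1, limit the mood entry to transient changes around a stimulation session, or remove it.
- In 19, state that mania or hypomania, worsening depression and suicidality are always entered on the AE eCRF with onset, severity, relationship and outcome, whatever the AEQ shows.
- Reconcile 19, 19.1, 19.2.2, 19.4 and 22.14: either the listings for all events cover only those on the AE form, with AEQ items tabulated separately, or the missing fields are collected for anticipated events too. Say what record the committee receives for an event captured only on the AEQ.
- Do not add mania or hypomania to the anticipated list. Under the present rules that would move it to the thinner route.
- Explain or resolve the difference between 9.1 and 19.1 on tinnitus and burns as housekeeping, bearing in mind that listing them would reduce what is recorded.

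The cost is wording plus a few extra AE forms, at visits where the relevant scales are already administered.

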19.2 CLASSIFICATION OF AN AE

19.2.1 SEVERITY

Investigators will assess the severity of the adverse event and classify it according to the following definitions:

- **Mild**: Awareness of a sign or symptom that does not interfere with the patient's usual activity or is transient, resolved without treatment and with no sequelae.
- **Moderate**: Interferes with the patient's usual activity and/or requires symptomatic treatment.
- **Severe**: Symptom(s) causing severe discomfort and significant impact on the patient's usual activity and requires treatment.

These definitions are for descriptive purposes only and are independent of the judgment of whether an event is classified as an AE or an SAE.

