22.14 SAFETY ANALYSES

Assessment of the safety of the investigational device will include an evaluation of the incidence and severity of complications and adverse reactions associated with the treatment.

Adverse event rates will be summarized by type of AE and for specific AEs in two ways:

- 1. per subject incidence of specific AEs and classes of AEs and
- 2. by event, summarizing event counts by visit interval over time and in accordance with FDA Guidance (CDRH 2004)¹⁵.

Device and procedure-related events will be summarized by severity and relatedness. Events listings that include details such as relatedness, severity, onset, and resolution status will be provided for all events and relevant subsets of events such as serious events and related events. Primary safety comparisons will be performed using the AT analysis set. The summary tables will show the adverse events (in coded terms), the total number of events, and the number and the percentage of subjects affected in each treatment group

¹⁵ CDRH. Guidance for Industry and FDA Staff: Clinical Data Presentations for Orthopedic Device Applications, December 2, 2004.

("subject wise evaluation") and stratified by relation to device and severity. Data of dropouts will be presented separately, and possible bias will be discussed in the final report.

All AEs will be summarized in listings for the AT analysis set. The following AE listings will be constructed:

- AE Listing 1 All AEs Sorted by Group and Event Type
- AE Listing 2 All AEs Sorted by Group and Subject
- AE Listing 3 Serious AEs
- AE Listing 4 Severe AEs
- AE Listing 5 Device Related AEs
- AE Listing 6 Serious Device Related AEs
- AE Listing 7 Severe Device Related AEs
- AE Listing 8 Other AEs
- AE Listing 9 AEs among subjects discontinued early
- AE Listing 10 AEs among subjects who died

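### The AE severity classes in section 19.2.1 overlap with no precedence rule, and Severe is closed to any event that required no treatment

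*Protocol*

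**What the plan says.** Section 19.2.1 of the protocol gives the scale and says who applies it: "Investigators will assess the severity of the adverse event and classify it according to the following definitions". There are three classes:

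- The lowest, Mild, can be reached in two ways: "Awareness of a sign or symptom that does not interfere with the patient's usual activity or is transient, resolved without treatment and with no sequelae".
- For the middle class, Moderate, either of two features is enough: "Interferes with the patient's usual activity and/or requires symptomatic treatment".
- The highest, Severe, needs all of its conditions at once: "Symptom(s) causing severe discomfort and significant impact on the patient's usual activity and requires treatment".

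The section gives no rule for an event that meets more than one class. It limits the role of the grades: "These definitions are for descriptive purposes only and are independent of the judgment of whether an event is classified as an AE or an SAE".

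Section 22.14 uses the grades: "Device and procedure-related events will be summarized by severity and relatedness". The adverse event tables are also stratified by severity, and AE Listings 4 and 7 cover Severe AEs and Severe Device Related AEs.

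Sections 19 and 19.1 split the recording. Unanticipated events go on the AE eCRF, where severity is a minimum field. Ten anticipated events, from headache to acute mood change, have their frequency and severity captured by the AEQ.

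**The concern.** A severity scale should place each event in one class, and its top class should be open to every event with the worst impact. This scale does neither. Mild has two routes joined by an *or*, and the second route (transient, untreated, no sequelae) does not mention impact. Moderate is met by any interference. Severe adds a treatment condition that has nothing to do with how badly the participant was affected.

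At stake is the descriptive safety profile. A disabling event that needed no treatment cannot appear in Listing 4 or Listing 7, whatever its impact. The trial has two sites in two countries, and the same event can be graded differently at each without either departing from the protocol. Investigators grade under the protocol as events occur, so a statistical analysis plan cannot repair the grades afterwards.

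**Working it through.** The protocol gives no figure to reproduce, so the check is a logical one. Each definition in section 19.2.1 is written as a condition and every possible event profile is tested against it.

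**Attributes (yes/no).** I = interferes with usual activity; S = significant impact; D = severe discomfort; T = transient; U = resolved without treatment; R = requires treatment; Q = sequelae.

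**Conditions.** The Mild sentence can be read in two ways.

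- Mild, reading A: not I, or (T and U and not Q).
- Mild, reading B: (not I, or T) and U and not Q.
- Moderate: I or R.
- Severe: D and S and R.

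**Profiles.** Two combinations are impossible: S without I, and U together with R. The pair (I, S) then has 3 allowed states, the pair (U, R) has 3, and D, T and Q have 2 × 2 × 2 = 8. That gives 3 × 3 × 8 = 72 profiles.

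**Severe discomfort and significant impact, no treatment required.** Here I = S = D = yes and R = no. T, U and Q are free, giving 2 × 2 × 2 = 8 profiles.

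- Severe: 0 of 8, because R fails.
- Moderate: 8 of 8, because I holds.
- Mild: 1 of 8 (T and U yes, Q no), under both readings.

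**Overlap in general.**

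- Mild and Moderate together: under reading A, 8 profiles that need treatment but do not interfere, plus 4 that interfere but are transient, untreated and without sequelae, so 12 of 72. Under reading B only the 4 remain.
- Moderate and Severe together: all 4 profiles that meet Severe. This is ordinary nesting in an ordered scale and is not a defect in itself.
- No class at all: 0 of 72 under reading A and 12 of 72 under reading B (no interference and no treatment required, but unresolved or with sequelae).

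These counts show which combinations the text mishandles. They are unweighted and say nothing about how often such events occur.

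**Which events use the scale.** The ten events listed in section 19.1 have their severity captured by the AEQ. Section 9.1 names device events that are not among the ten: increased tinnitus (Table 4, 0.45% of users) and small skin burns (no rate given). If the Table 4 rate applied to all 270 subjects, tinnitus of any severity would be expected in 0.0045 × 270 = 1.2 of them. The documents give no rate for disabling, untreated events.

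**Effect of the correction.** A highest-class-met rule alone would move the doubly graded event from Mild/Moderate to Moderate, but Severe would stay at 0 of 8. If Severe becomes D and S, all 8 reach Severe. If Mild becomes not I, every profile has a class, since I = no gives Mild and I = yes gives Moderate. The 8 profiles that need treatment without interference then resolve to Moderate under the precedence rule.

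**The case against.** The strongest reply is that little depends on this scale. The protocol calls it descriptive and separate from AE/SAE classification. The stopping rules, treatment-failure withdrawal, SAE reporting and UADE determination do not use it. The same definitions apply in both arms. All of this stands, and it is why the point is minor. It does not remove the grades from the section 22.14 tables and listings.

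A second reply is that Mild opens with mere awareness of a symptom, so a sensible investigator would not call a disabling event Mild. That is a reasonable reading, and Mild is never forced, since the same event always meets Moderate. But nothing in the text directs the choice, and no reading of Mild opens Severe to an untreated event. The Clinical Events Committee adjudicates all AEs under section 19.4, but no other scale is given for it.

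A reader might infer more than the documents support:

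- *That the commonest device effects are under-graded.* Their severity is captured by the AEQ. Skin redness is on that list, and nothing describes it as disabling.
- *That the treatment-emergent mania or hypomania cases in section 9.1 illustrate the fault.* The protocol says of them: "The observed cases have also been mild and in general not required any intervention". A mild grade for a mild case is not under-grading.
- *That a self-limiting event can never be Severe.* This holds only if no treatment was required. An event that would have passed alone but still required treatment can be graded Severe.
- *That a Severe grade cannot be checked because treatment is not recorded.* Section 19 lists minimum eCRF fields only, and the form is not shown. A treatment-given field would also not settle whether treatment was required, which is a judgement.

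**Conclusion.** Wrong as written, minor. Under either reading of Mild, an event with severe discomfort and significant impact that required no treatment cannot be graded Severe. If it was also transient and without sequelae, it meets both Mild and Moderate, with no rule to choose between them.

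The consequence is possible under-counting and inconsistent grading in the severity-by-relatedness summary and in AE Listings 4 and 7. It falls mainly on unanticipated events on the AE eCRF, including known device events outside the AEQ list. Section 19.2.1 does not itself restrict its scope, so *mainly* is as far as this can be taken. The number of events affected cannot be estimated from the protocol. The conclusion assumes that investigators apply the definitions literally and that tinnitus and skin burns are recorded on the AE eCRF because section 19.1 does not list them. It does not extend to SAE classification, the stopping rules or the primary endpoint.

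**What to change.** Amend section 19.2.1 as follows:

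- State that the highest class met applies.
- In Mild, limit the clause on transient, untreated events without sequelae to events that do not interfere with usual activity. Word it as description and not as a further requirement, so that a persistent but non-interfering event still has a class.
- In Severe, remove treatment as a necessary condition.
- In Moderate, keep the symptomatic-treatment route. Without it, an event that needs treatment but does not interfere would fall from Moderate to Mild.

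Optionally, add treatment given as a field on the AE eCRF.

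The cost is minor rewording and investigator retraining. Some events will move to a higher grade, so the reported safety profile will look slightly less favourable. Sample size, visits and treatment do not change.
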